### 9.0 Reportable Events

The PI will report any adverse event or unanticipated problems involving risk to the IU IRB through the Quali Coeus system. Collection of adverse and serious adverse events will begin to be collected at the time of consent. Events that will be promptly reported include anything that would impact subject safety, confidentiality, information security, or privacy. In the scope of this research study, the following events would be considered **promptly reportable** within 5 business days of the investigator becoming aware of the event:

1. Serious adverse events assessed by the PI as 1) unexpected, 2) related or possibly related to study participation, and 3) suggests that the research places subject(s) at greater risk or harm than previously anticipated. These may include injuries (e.g. broken bone) or medical events (e.g. chest pain) that meet the following criteria;
  - a. Are life-threatening or result in death
  - b. Causes disability or incapacity
  - c. Requires in-patient hospitalization
  - d. Results in a congenital anomaly and/or
  - e. Considered an important medical event
2. Although not anticipated to occur, any major protocol deviations or noncompliance by an investigator involved with conducting research that in the opinion of the PI 1) impacted subject safety, and/or 2) affects the integrity of the data. These may include:
  - a. Dosage errors with beetroot juice (nitrate) supplementation, enrolling of a subject who fails to meet inclusion criteria, and/or study visits performed outside of the outlined timeframe in the protocol document
3. Although not anticipated to occur, any incident that breaches subject privacy and/or confidentiality (i.e. loss of information containing identifiable records) would be considered a promptly reportable event. Any such incident would also be reported to the HIPPA Privacy Office.
  - a. IU HIPPA Privacy Officer: [contact]
4. Exceeding the study-wide enrollment number (i.e. 50 subjects).
5. Implementation of major changes (i.e. study procedures, risks and/or benefits) to the study protocol or documents without IRB approval.
6. Conduct of research procedures including interaction with subjects or review of identifiable subject information by individuals who are not listed as approved personnel and have not completed the necessary CITI training.

Additionally, events that do not meet prompt reporting criteria, but are still considered reportable will be communicated to the IU IRB at the time of the next study renewal. These events would include:

1. Local adverse events, which were not previously promptly reported and occurred at a greater frequency and/or severity than was initially anticipated. In relationship to the relevant study procedures, this may include:
  - a. A greater frequency and/or severity of symptoms related to beetroot juice ingestion (e.g. gastrointestinal distress), muscle soreness during the walking and/or muscle strength tests, discomfort or bruising with needlestick blood draws.
  - b. Injuries or medical conditions that do not require hospitalization and are not considered medically important (e.g. twisted ankle, sore muscles/joints, pulled muscle).
  - c. Enrollment of a greater number of subjects that does not exceed the total study-wide enrollment number (i.e. 37-50 subjects enrolled).
  - d. Conduct of research procedures by individuals who are not listed as approved personnel on the study protocol.
  - e. Implementation of minor wording changes to study documents.

### **10.0 Data Safety Monitoring**

[name] (Department of Kinesiology) will work with [name] (Department of Kinesiology) to oversee aspects of data management and safety monitoring for the current investigation, including: data quality, subject recruitment, accrual, retention, outcome and adverse event data. Both are independent of the PI and funding source. [name] is not directly affiliated with the study but will be responsible for performing periodic inspection of data quality and random assessments of participant recruitment, retention, adherence, and adverse events.

[name] and [name] will hold in-person meetings once every 3 months to address items related to data quality. However, [name] will perform periodic assessments at random to examine participant recruitment, retention, adherence, and adverse events.

As a safety precaution, potential side effects of acute beetroot juice ingestion will be determined for each participant during visit 1. Stopping criteria will be instituted (i.e., participant withdrawn) if a participant exhibits, during a 3-hr period, either a drop of >20 mm Hg in systolic blood pressure or a value of 12% in blood methemoglobin (determined via CO-oximeter).

Statistical analyses will be conducted on validated statistical software (e.g. SPSS, SigmaPlot) and results will be reported through traditional scientific outlets such as peer-reviewed journals and presentations. All analyses will be done without the use of any identifying features to individuals enrolled (e.g. use of ID codes, saving electronic data using ID codes rather than subject name).

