### **2.2 Secondary Objective**

**Aim 2a.** Determine preliminary effects sizes for pre-exercise beetroot juice consumption + exercise training (BR+EX) compared + exercise training only (EX) on distance (feet) covered during a 6-minute walk test. Performance during the 6-minute walk has been shown to accurately estimate peak oxygen uptake (i.e., aerobic fitness) and functional mobility. Consistent with others showing performance benefits of pre-exercise beetroot juice consumption and acute exercise, we anticipate a small to medium effects size in a beneficial direction (i.e., greater positive change) for BR+EX compared to EX.

**Aim 2b.** Determine preliminary effect sizes for BR+EX compared to EX on improvement of endothelial-dependent vasodilation as evidenced by percent increase in flow-mediated dilation. Based on our working premise that beetroot juice may offset the burdens of endothelial dysfunction/activation by increasing nitric oxide bioavailability, coupled with the effects of exercise training, we anticipate a small to medium effect size in a beneficial direction for BR+EX compared to EX.

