## 5.0 Study Design

To fulfill the purposes outlined above, a 2-arm randomized controlled study design will be employed. After completing initial screening procedures (**screening visit**), subjects will return

to the School of Public Health at Indiana University Bloomington to have baseline measures of weight, body composition, bone density, heart rate, cutaneous vascular conductance, blood pressure, assessed prior to and 3-hours following ingestion of beetroot juice (**Visit 1**). During this visit, two questionnaires will be administered to obtain information related to the health history, physical activity habits, mood state, and cognitive abilities of the subjects. Following a minimum 7-day washout period, to mitigate the risk of any carry-over effect from the acute dose of beetroot juice administered during the initial visit, subjects will have their blood drawn at the Indiana University Student Health Center followed by measures of weight, body composition, and pulse wave velocity performed at the School of Public Health at Indiana University Bloomington (**Visit 2**). During this visit they will also perform two 6-minute walking tests, and muscle function test. After baseline assessments **Visits 1-2**, participants will be randomly assigned to one of two study arms. All study arms will complete an 8-week exercise training protocol. The first arm will serve as a control group and will require participants to only complete the 8-week exercise training protocol (EX). The second arm will complete exercise training with ingestion of a beetroot (BR+EX). Exercise training will occur no more than 6 weeks following baseline Visit 2 to minimize the effects of potential changes in physical conditioning/deconditioning on baseline measures. Subjects will be asked to repeat baseline Visit 2 before initiating exercise training in the event >6 weeks lapses from the completion of the final baseline assessment visit.

The same procedures as performed in **Visits 1-2** will be repeated following the treatment intervention for **Visits 3-4** in reverse order. The procedures outlined for **Visit 2** will be performed during **Visit 3**, and procedures for **Visit 1** for **Visit 4**.

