Participants will perform baseline assessments (**Visits 1-2**) prior to randomization. Subsequently, participants will be randomly selected to: 1) control (EX only) or 2) BR+EX. Group allocation will be determined at random using a computer-based number generator in blocks of 2 to ensure equal between-group distribution (i.e.  $n = 2$  Ex only;  $n = 2$  BR+EX). Each number will be kept in a sealed envelope until completion of **Visits 1-2**.

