**Pulse Wave Velocity (PWV)**- Measurements of PWV (m/s) will be obtained from standard blood pressure and tonometry assessment using the ATCOR SphygmoCor device. This device is a non-invasive way to perform central blood pressure waveform assessment. During **Visits 2 and 2**, subjects will be asked to lie still in a supine position on a padded table surface for a duration of 10 minutes. A leg blood pressure cuff will be placed on the upper thigh. A technician will apply carotid tonometry simultaneously to inflating the blood pressure cuff to obtain blood pressure waveforms at the carotid and femoral artery sites. SphygmoCor software uses physical distance measurements between the sites to calculate velocity.

**Laser Doppler Blood Flow Heating Protocol**- Laser Doppler (Blood FlowMeter, Ad Instruments) will be used to assess cutaneous vascular conductance in response to a localized heating stimulus. Two small skin surface probes will be applied to the non-dominant forearm of the subject during **Visits 1 and 4**. Resting measurements will be obtained for 5 minutes followed by a measure of resting blood pressure. Localized skin heating will be accomplished with local heating units that will surround the skin surface probes of the laser Doppler. Both probes will be heated to a set temperature of 39°C (102°F) for 25 minutes. . The temperature of the probes will then be increased until a maximum temperature of 44°C (111°F) and held for 15 minutes . Blood pressure measurements will be obtained from the dominant arm every 10 minutes during the 40-minute heating protocol. From measures of blood pressure and the laser Doppler blood flow, cutaneous vascular conductance will be calculated as a ratio of skin blood flow to mean arterial pressure. Cutaneous vascular conductance will be expressed as a percentage of maximal conductance measured at the end of the heating protocol.

**Blood Pressure**- Blood pressure readings (mm Hg) of systolic and diastolic blood pressure will be taken using an automated sphygmomanometer on the dominant upper arm. During **Visits 1 and 4**, measurements will be taken during seated rest, every 10 minutes during the localized heating protocol, and every hour for 3-hours following ingestion of beetroot juice. During **Visits 2 and 3**, measurements will be taken during standing rest prior to the submaximal walking exercise, at minutes 3 and 5 during submaximal walking, and after 3 minutes of recovery following submaximal walking.

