**6-Minute Walk Test-** Consistent with standard procedures (20), participants will be instructed to walk for six minutes around an indoor, closed course during **Visits 2 and 3**. A chest-strap heart rate monitor will be worn to measure changes in heart rate before and after walking, and a triaxial accelerometer will be used to examine signal profile associated with movement complexity (i.e. movement accelerations) and estimates of energy expenditure (kilocalories). The accelerometer will be worn on the non-dominant hip and fastened with an elastic belt. Subjects will additionally be asked to identify their level of perceived exertion on a continuous visual analog scale (“no exertion” to “maximal exertion”) after the test.

**Supervised Exercise Training (CrossFit, Bloomington)-** Participants randomized to exercise training will perform combined aerobic and resistance workouts in a group setting with a cohort of approximately 4 women also enrolled in the study. There is a chance that participants will complete the exercise training sessions with other individuals who are not enrolled in the study. This will be outlined in the Informed Consent Statement provided to participants.

Full participation in the exercise training intervention is defined as attending 3 sessions per week for a total of 8 weeks (24 sessions total). The sessions will be supervised by a certified fitness professional who will make adjustments to the workouts based on individual needs/abilities. Each one-hour session will consist of a warm-up, instruction of the workout, a workout of combined aerobic and resistance training exercises, and cool-down. Intensity of the exercise sessions will be progressed gradually from weeks 1 to 8 and monitored by having participants identify their rating of perceived difficulty for each session using a discrete visual analog scale (0-10). The intensity of exercise sessions will also be monitored through continuous heart rate assessment (Actiheart) during week 2, week 4, and week 6 of training.

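### Nothing in the visible plan keeps follow-up testers or trace processing unaware of arm, which exposes the Aim 2 effect sizes to assessor bias of unknown size

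*Combined protocol and SAP*

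**What the plan says.** **Arms.** Section 5.0 describes the control as follows: "The first arm will serve as a control group and will require participants to only complete the 8-week exercise training protocol (EX". Of the other arm it says: "The second arm will complete exercise training with ingestion of a beetroot (BR+EX". No placebo or sham drink is described.

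**Concealment.** Section 6.0 provides for the allocation numbers: "Each number will be kept in a sealed envelope until completion of" Visits 1-2. No later concealment is described.

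**Follow-up visits.** Section 5.0 reverses the order of the baseline visits: "The procedures outlined for Visit 2 will be performed during Visit 3, and procedures for Visit 1 for Visit 4". The calendar in Section 8.0 marks test-day juice only at the first baseline visit and the last follow-up visit.

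**Coding.** Section 10.0 says: "All analyses will be done without the use of any identifying features to individuals enrolled (e.g. use of ID codes". Section 14.0 gives each participant a unique ID and de-identifies samples and data with it.

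**Measurement (Section 7.0).** For the 6-minute walk, "participants will be instructed to walk for six minutes around an indoor, closed course". For pulse wave velocity, "A technician will apply carotid tonometry simultaneously to inflating the blood pressure cuff". Dynamometry recordings are trimmed to the constant-velocity portion and smoothed in a spreadsheet.

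**The concern.** In a trial with no comparator drink, participants know their arm and so do the staff who supply the juice. If whoever runs the walk, holds the tonometer or trims a trace also knows the arm, then instruction, technique and handling can drift towards the hoped-for result. Section 2.2 states that a benefit for BR+EX is expected, so such a drift has a likely direction.

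This matters because Section 12.0 wants preliminary effect sizes for a larger study, and Section 3.2 calls the secondary outcomes successful on statistically significant gains over EX. A systematic error enters Cohen's d directly, and recruiting more women does not dilute it.

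**Working it through.** The plan gives no figure on this point to reproduce. The check is whether any text closes each route by which arm could reach an assessor.

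1. **Can participants be masked?** No. EX receives nothing to drink. The plan does not call itself open-label; that is an inference from the arms in Section 5.0.

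2. **Do staff learn the arm?** Some must. Section 7.0 has juice handed out and resupplied halfway, and has a team member drop in during weeks 3 and 6 to check supplement compliance by breath test.

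3. **Does concealment reach follow-up?** No. The envelopes are opened once Visits 1-2 are done. Baseline is protected; Visits 3 and 4 are not.

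4. **Do the ID codes hide arm?** Not by any stated rule. Sections 10.0 and 14.0 replace names. Nothing suggests that the ID encodes arm, but nothing says that arm is withheld from those handling coded files.

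5. **Is masking stated anywhere else?** No visible section says that testers, trace readers, the laboratory or the analyst are unaware of arm. The title pages were removed, so a statement there cannot be excluded; Sections 6.0, 7.0, 10.0 and 12.0 would still lack the operating rule.

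6. **Which outcomes are exposed?** The 6-minute walk (effort under staff instruction), tonometry (operator technique) and dynamometry (effort, then trace handling). Plasma markers are less exposed. Flow-mediated dilation is named in Section 3.2 but has no procedure in Section 7.0 and no calendar row, so its reader cannot be checked.

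7. **Could testers be masked in this design?** Yes. Visit 3 repeats Visit 2 and involves no juice. At Visit 4 the calendar marks acute juice without restriction by arm, so drinking it reveals nothing. The visit labels conflict: Section 7.0 puts pulse wave velocity at Visit 2 twice, and the calendar numbers the follow-up visits 1 and 2. These need reconciling, but Section 5.0 and the calendar rows agree that the follow-up walk visit has no juice.

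8. **Can the bias be sized?** Write the expected observed effect as d = δ + b_participant + b_assessor, all in SD units. The documents give no value for either bias term, and masking assessors acts only on the last one. For scale, the sampling error of d is about √(2/n) with n per arm:
   - 20 completers (Section 3.1), n = 20/2 = 10: √(2/10) = 0.45
   - 24 randomised (Section 3.1), n = 24/2 = 12: √(2/12) = 0.41
   - 36 enrolled (Section 6.0), n = 36/2 = 18: √(2/18) = 0.33

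   These assume equal arms, and for the last that all 36 are randomised. Sampling error falls as n rises; the bias terms do not.

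**The case against.** **Masked testers miss the main route for the walk.** Effort and expectancy on the participant's side cannot be masked here. This stands: the fix removes assessor bias only.

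**Discretion is limited.** Software computes pulse wave velocity, blood pressure is automated, skin conductance is a defined ratio, the dynamometry filter is fixed, and the walk follows a cited standard that cannot be inspected here. Knee extension is not in the Section 3.2 success rules; leg strength appears only in the Section 12.0 regression. This stands in part. It narrows the exposure without closing it: a technician still applies the tonometer, staff still instruct the walk, and traces are still trimmed.

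**Files are already coded.** Section 14.0 does this. It stands, so only the rule on when arm is merged is new.

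**It is a feasibility pilot.** Section 12.0 disclaims confirming efficacy, and project success is 20 of 24 completing. This limits the weight of the point. Effect sizes are nevertheless a stated product, and Section 3.2 does judge by significance.

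Three stronger readings are tempting but unsupported:

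- *Arm knowledge inflates d by a given amount, perhaps enough to mimic the small effect of 0.2.* The documents give no bias estimate and nothing to split it between participant and assessor. Any such figure would be assumption plus addition.
- *The plan attributes any difference to nitric oxide.* Section 2.2 says only "Based on our working premise that beetroot juice may offset the burdens of endothelial dysfunction/activation by increasing nitric oxide bioavailability", and pairs it with the effects of training. That is a premise, not a commitment on interpretation.
- *The staff who supply juice also run Visit 3.* The documents do not say who does what. The gap is that nothing prevents it.

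**Conclusion.** The omission is real. After baseline, no visible rule keeps testers or those processing traces unaware of arm, and the ID codes serve confidentiality. The Aim 2 estimates are therefore open to assessor bias, with a likely direction in favour of BR+EX but a size that the documents do not allow one to state. The feasibility aim is largely unaffected.

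This is a cheap improvement, not a defect that invalidates the pilot. It rests on two assumptions: that the removed pages contain no operating rule for masking, and that the calendar means what it shows at the last follow-up visit, namely juice for both arms.

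**What to change.** 1. **Sections 7.0 and 12.0:** require dynamometry windowing, and any other processing of dynamometry, laser Doppler, tonometry and accelerometer files, to be completed and locked under the existing ID codes before the arm key is merged. This works even where tester masking fails.
2. **Section 7.0:** where existing staffing allows, have Visit 3 and Visit 4 tests run by team members who neither hold the allocation list nor supply juice, and ask participants not to mention their arm.
3. **Sections 3.2 and 12.0:** state that the contrast is open-label juice plus training versus training alone, and that participant expectancy remains in the effort-dependent outcomes.

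Cost: a processing rule, a sentence on interpretation and some scheduling inconvenience. No visit, measurement or participant is added. Whether step 2 can be met in full depends on staffing that the documents do not describe, and women may still disclose their arm.

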### **11.0 Study Withdrawal/Discontinuation**

A subject may elect to discontinue with study procedures by verbally notifying a member of the research team that they would like to do so either in person or by phone. Contact information for [name] and [name] is provided in the Informed Consent Statement. All

members associated with the research study (i.e. fitness instructors at Crossfit Bloomington) will be instructed to notify the research team in the event of a subject dropout.

Subjects may be withdrawn from the study by members of the research team if it is determined their safety is at risk (e.g.  $>20$  mm Hg drop in systolic blood pressure with acute beetroot juice ingestions), they are unable to perform procedures as requested, or fail to follow instructions provided. Additionally, subjects may be withdrawn if they miss (do not attend) more than 3 consecutive exercise training sessions in any given week of the supervised exercise training protocol. Withdrawal is also warranted if they attend less than 70% of the scheduled exercise training sessions (e.g. less than 17 out of the 24 total sessions).

### **12.0 Statistical Considerations**

Rather than confirm efficacy, this proposal addresses elements of feasibility such that we intend to generate preliminary effect sizes for a larger-scale investigation. Descriptive statistics and calculation of rates (e.g., recruitment, retention, adherence, and adverse event) will be used for study aim 1. Between-group differences in descriptive data along with aims 2(a,b) and 3 will be evaluated using an unpaired t-test. Effect size calculations will be performed with Cohen's  $d$  to qualify substantive differences: small (0.2), medium (0.5), and large (0.8). Potential covariates of interest include age, body mass, body fat percentage, and/or markers of inflammation. Non-normally distributed data will be log-transformed. Two-tailed parametric correlations (Pearson) will be performed and based on consequent results, multiple linear regression will be used to examine changes in inflammation, endothelial function, distance in 6-minute walk test, leg strength, and resting blood pressure/arterial stiffness.

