### **3.0 Outcome Measures/Endpoints**

#### **3.1 Primary Outcome Measures**

Outcomes of interest include recruitment, retention, adherence (i.e., exercise prescription and assessments), perceived exercise difficulty, and adverse event rates. Project success will be based on 83% [20 of 24] of randomized participants completing 8 weeks of exercise training.

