#### **3.2 Secondary Outcome Measures**

**2a.** The distance (feet) covered during a 6-minute walk test at baseline prior to the intervention and following BR+EX is the main secondary outcome of interest. To confirm the relationship of the functional 6-minute walk test to aerobic fitness, measures of oxygen consumption (ml/kg/min or L/min), heart rate (bpm), and blood pressure (mm Hg) will be taken during constant speed walking at a typical walking pace prior to the 6-minute walk test. Additionally, functional mobility will be assessed by analyzing triaxial movement patterns from an accelerometer worn on the non-dominant hip during the 6-minute walk test.

The BR+EX intervention will be considered successful in the event that there is a statistically significant increase in 6-minute walk distance (feet) along with a decrease in oxygen consumption (ml/kg/min or L/min), decrease in exercising heart rate (bpm), improvement in heart rate recovery following exercise (post exercise heart rate – heart rate 1 min, 2 min after exercise (bpm)), decrease in exercising blood pressure (mm Hg), decrease in post-exercise blood pressure (mm Hg), and/or improvement in gait function (i.e. preferred walking speed, center of mass characteristics) from baseline to post-intervention above any improvement seen in EX.

**2b.** Percent changes in brachial artery diameter (%), cutaneous vascular conductance (%), and pulse wave velocity (m/s) at baseline prior to the intervention and following BR+EX are secondary outcomes of interest, representing changes in endothelial dependent vasodilation. A non-invasive technique of flow mediated dilation of the brachial artery using ultrasound imaging will be used to assess the percent change in vessel diameter following occlusion. A local heating protocol using non-invasive Laser Doppler flowmetry in conjunction with blood pressure measurements will be used to obtain measures of red blood cell (RBC) flux and mean arterial pressure (MAP) to calculate cutaneous vascular conductance (RBC flux/ MAP). The velocity of the pulse wave traveling from the carotid to femoral artery will be assessed non-invasively using tonometry.

A statistically significant increase in the percent change in brachial artery diameter (%), cutaneous vascular conductance (%), and/or a decrease in pulse wave velocity (m/s) in BR+EX above any improvement observed in EX from baseline to post-intervention will be considered a successful outcome.

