### 3.3 Tertiary/Exploratory/Correlative Outcome Measures

Tertiary outcome measures of interest include plasma concentrations of sICAM-1, s-VCAM-1, sNCAM, MPO, IFN $\gamma$ , IL-1 $\beta$ , BDNF, TNF- $\alpha$ , and IL-10 obtained from a venous blood sample taken at baseline and post-intervention.

Statistically significant decreases in endothelial microparticle concentrations from baseline to post-intervention in BR+EX that are above any decrease observed in EX will be considered a successful outcome.

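### The arm comparison for Aims 2a, 2b and 3 does not adjust for each outcome's own baseline value, so a valid test usually gives less precise effect estimates than the collected data allow

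*Combined protocol and SAP*

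**What the plan says.** The analysis plan is a single paragraph in Section 12.0. Its purpose is stated as: "we intend to generate preliminary effect sizes for a larger-scale investigation". For the arm comparison it says: "Between-group differences in descriptive data along with aims 2(a,b) and 3 will be evaluated using an unpaired t-test". Cohen's d is then computed and labelled small, medium or large at 0.2, 0.5 and 0.8. The paragraph does not say whether the t-test is applied to follow-up values or to changes, and it does not name the SD that divides the difference in d.

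Other sections point to change scores. Section 2.2 expects an effect "in a beneficial direction (i.e., greater positive change) for BR+EX compared to EX". Section 3.2 judges the walk-test result "from baseline to post-intervention above any improvement seen in EX", and Section 3.3 looks for decreases in the blood markers "from baseline to post-intervention in BR+EX that are above any decrease observed in EX".

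On adjustment, Section 12.0 says: "Potential covariates of interest include age, body mass, body fat percentage, and/or markers of inflammation". It adds that, depending on Pearson correlation results, "multiple linear regression will be used to examine changes in inflammation, endothelial function, distance in 6-minute walk test", together with leg strength and resting blood pressure or arterial stiffness.

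The baselines exist. Sections 7.0 and 8.0 place the walk test, pulse wave velocity and blood draw at one baseline and one follow-up visit. Skin conductance is measured before and 3 hours after juice at the other pair of visits.

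**The concern.** Subtracting the baseline is not the same as adjusting for it. A change score fixes the baseline coefficient at 1, whereas ANCOVA estimates it. When the true slope is well away from 1, the change score carries extra noise.

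Nothing in Section 12.0 fills the gap. The listed covariates are only potential. Age, body mass and body fat are not the outcomes' own baselines. Markers of inflammation may overlap some Aim 3 outcomes, but they are optional and not said to be baseline values. Baseline walk distance, pulse wave velocity and skin conductance are absent. The regression on changes is conditional on earlier results and names neither an arm term nor a baseline term, so it is not a pre-specified adjusted comparison.

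What is at stake is precision in the quantity that Aims 2 and 3 are meant to deliver. With about 20 completers that precision is poor, so any that is available from data already in hand is worth taking.

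**Working it through.** The documents give no SD, correlation, power or sample-size calculation for Aims 2 and 3, so there is no stated figure to reproduce.

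**Inputs from the documents**
- Completers: Section 3.1 says "Project success will be based on 83% [20 of 24] of randomized participants completing 8 weeks of exercise training". 20/24 = 83.3%; with equal allocation, n = 10 per arm.
- Alternatives: n = 12 per arm if all 24 complete; n = 15 if 83% of the 36 in Section 6.0 complete (36 × 0.833 = 30); n = 18 if all 36 do.
- Section 7.0 requires 17 of 24 sessions for follow-up assessment, so completers approximate the analysed number.

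**Assumptions (not in the documents)**
- r = baseline-to-follow-up correlation, 0.3 to 0.9.
- k = follow-up SD divided by baseline SD: 1, 0.8 or 1.25.

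**Formulas** (95% CI half-width, in baseline SDs)
- Change-score t-test: t(2n−2) × √(2/n) × √(1 + k² − 2rk)
- ANCOVA: t(2n−3) × √(2/n) × k√(1 − r²) × √(1 + 1/(2n−4)); the last factor is the expected cost of estimating the slope.

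**Example, n = 10, k = 1, r = 0.5**
- Change: 2.101 × 0.447 × 1.000 = 0.940
- ANCOVA: 2.110 × 0.447 × 0.866 × 1.031 = 0.842
- 0.842/0.940 = 0.896, or 10.4% narrower.

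**Results, n = 10 per arm**

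| r | Change, k = 1 | ANCOVA, k = 1 | Effect of ANCOVA, k = 1 | k = 0.8 | k = 1.25 |
|---|---|---|---|---|---|
| 0.3 | 1.112 | 0.928 | −16.5% | −26.7% | −8.3% |
| 0.5 | 0.940 | 0.842 | −10.4% | −21.8% | −2.2% |
| 0.7 | 0.728 | 0.695 | −4.6% | −18.0% | +2.5% |
| 0.8 | 0.594 | 0.584 | −1.8% | −17.2% | +3.5% |
| 0.9 | 0.420 | 0.424 | +0.9% | −19.3% | +0.9% |

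Negative means a narrower interval.

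**Sensitivity to n** (k = 1; r = 0.3/0.5/0.7/0.9). The effect is −17.2/−11.0/−5.3/+0.2% at n = 12, −17.7/−11.6/−5.9/−0.5% at n = 15 and −18.0/−12.0/−6.3/−0.9% at n = 18. The conclusion does not depend on which enrolment figure applies.

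**Validity.** In a 20,000-replicate simulation (k = 1), coverage was 94.8% to 95.3% for both methods.

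**If the t-test were meant for follow-up values.** At n = 10 and k = 1 the half-width ratio of ANCOVA to that test is (2.110/2.101) × 1.031 × √(1 − r²) = 1.035 × √(1 − r²). This is 3.5% wider at r = 0, but 1.035 × 0.866 = 0.896 at r = 0.5 and 1.035 × 0.714 = 0.739 at r = 0.7.

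**The SD behind d.** With k = 1 the change SD is √(2(1 − r)) baseline SDs. A raw difference of 0.3 baseline SD is therefore d = 0.25, 0.30, 0.39 and 0.67 on the change SD at r = 0.3, 0.5, 0.7 and 0.9. The same effect can fall on either side of the 0.5 label according to the SD used.

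**The case against.** The strongest reply is that nothing is broken. The planned test is valid, the primary aim is feasibility and is untouched, and the choice is between two legitimate analyses. The gain rests on an r and k that the documents do not supply. It is under 5% at r = 0.7 or above with equal SDs, and with a larger follow-up SD it turns into a small loss at r = 0.7 and above. Sampling error dwarfs it: an observed d of 0.30 at 10 per arm has standard error √(2/10 + 0.09/40) = 0.450 and an approximate 95% CI of −0.58 to 1.18. All of this stands, and it limits the point to an improvement in precision. It does not remove it: the losses computed are small, the possible gains are several times larger, and the change needs no new data.

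A reader might infer two stronger things.

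- *Chance imbalance biases the comparison.* A baseline gap above 0.5 SD has probability 26% at 10 per arm, and at r = 0.7 a gap of exactly 0.5 SD shifts the change comparison by 0.5 × (0.7 − 1) = −0.15 SD. That variation is already inside the change-score standard error, which is why coverage is correct. It is the same inefficiency seen another way.
- *An undefined d will leave the larger trial underpowered.* The documents do not support this. Each d is right for its own analysis, harm needs a future team to mismatch the two, and the change-based wording of Sections 2.2, 3.2 and 3.3 makes the pooled change SD the likely default. At r = 0.5 and equal SDs the two versions of d coincide.

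**Conclusion.** The point holds as a precision improvement over a valid test. At 10 completers per arm with equal SDs, ANCOVA on the outcome's own baseline changes the 95% CI half-width by between −16.5% (r = 0.3) and +0.9% (r = 0.9). Across the assumed SD ratios the range runs from 27% narrower to 3.5% wider, the latter at r = 0.8 with a follow-up SD 1.25 times baseline. These figures rest on assumed r and k, roughly equal arms, and the change-score reading of Section 12.0. The replacement of the t-test is the substantive part; naming the SD for d is a secondary reporting clarification. The change should be made, because effect estimates are the stated output of Aims 2 and 3, but the plan is not in error without it.

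**What to change.** In Section 12.0, for each Aim 2 and Aim 3 outcome measured at both baseline and follow-up, replace the unpaired t-test with ANCOVA of the follow-up value on arm and that outcome's own baseline value.

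- **Skin conductance:** state whether the pre-juice or post-juice reading is analysed, and use the matching baseline reading.
- **Flow-mediated dilation:** it has no procedure entry in Section 7.0 and no row in the Section 8.0 calendar, so this applies only if it is measured at both times.
- **Further covariates:** take any from baseline.
- **Reporting:** give the adjusted difference with 95% CI in original units or, where both values are logged, as a ratio of geometric means.
- **Cohen's d:** compute it on the analysis scale with one pre-stated SD, for example the pooled baseline SD, and report the baseline, follow-up and change SDs beside it. Those three SDs determine r within each arm, so later designers can convert.

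The cost is SAP wording and one degree of freedom, with no new data, visits or change to randomisation. In the least favourable case computed against the change-score test, intervals are about 3.5% wider.
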